### 9.3.2 Entomological samples

Collected mosquitoes will be returned to the laboratory for morphological identification, sporozoite ELISA testing, and, if necessary, species identification by PCR

### 9.3.3 Sample storage and shipping

#### 9.3.3.1 Storage

All filter papers with DBS will be stored at the KEMRI CGHR campus in Kisian until the end of the study. All laboratory tests, as part of primary and secondary analyses, can be performed at the Kisian campus. For laboratory studies that may not be available at the Kisian campus, samples from participants who consent to shipment of samples may be shipped to laboratories at the CDC in the United States or to laboratories in the United Kingdom at the Liverpool School of Tropical Medicine.

For participants who consent, samples will be stored for up to 25 years from the time that the study ends. This is because the technology for sequencing parasites for clonal diversity, resistance, and serological markers of exposure is rapidly advancing. It may prove useful to analyze stored samples at a later date. At the end of the 25-year period, all biological specimens will be destroyed. Remnants of samples shipped to another laboratory will be destroyed after the testing has been completed.

#### 9.3.3.2 *Shipping*

All specimens to be shipped will be packaged, shipped, and transported according to the current edition of the International Air Transport Association (IATA) Dangerous Good Regulations as at the time of shipping.

## 9.4 STATISTICAL METHODS

### 9.4.1 Interim analysis

#### 9.4.1.1 *Purpose of the interim analysis*

The study is designed to have two interim and one final analysis, i.e. a total of three looks. The timing of the interim analysis is based on the number of cumulative events or person time accumulated as described in section 6.2.2, Duration of trial, interim analysis and criteria for early termination, page 17. In brief, the interim analyses will occur either after 50% and 75% of person-time have completed (i.e., after about 1 and 1.5 years respectively), or after 50% (n=372) and 75% (n=558) of the total number of expected primary outcome events over two years in the control arm (n=744) have occurred (whichever comes first).

The purpose of the interim analysis is to use the preliminary data to inform the assessment process by WHO's Vector Control Advisory Group (VCAG) in a timely manner. This requires at least a single year of data, but ideally, two years [18]. This study in Kenya is part of three similar trials conducted in Kenya (this protocol), Zambia and Mali. The combined results will inform WHO's recommendation process regarding ATSBs. Each of these three trials is designed to have an interim analysis. A decision to stop any of these three trials, including this one, early for overwhelming evidence of efficacy will depend on the overall evidence from the three trials and thus not only on the evidence generated from a single trial. It is thus possible that WHO's VCAG, the DSMB and/or the trial steering committee will recommend continuing this trial in Kenya for the full two years even if statistically the stopping boundary is crossed (suggesting overwhelming evidence of efficacy) or there is evidence of futility. The possible rationale for any of these committees to recommend continuing the trial for a second year may involve continuing collecting more epidemiological, entomological, behavioural, and safety information and data for further subgroup analyses. This would allow determining the cumulative effects of the intervention over a two-year period as behavioural changes of the population (e.g., change in adherence to the deployment of ATSBs), year-to-year seasonal variation in malaria transmission, cumulative impact on mosquito densities and community-effects, etc., may impact on the results over time.

However, it will also be possible that these committees recommend stopping the trial early if the committees agree that sufficient evidence is available after the first or second interim analysis to make a recommendation. This is the rationale to design the study to allow for two interim analyses.

#### 9.4.1.2 *Procedures for interim analysis*

The interim analysis will be conducted on the primary endpoint using the intention-to-treat analysis population. First, the trial statistician will develop the analysis programs for the primary outcome

and validate them using a test version of the study database with a dummy random treatment code. Then, these programs will be provided to the DSMB statistician before the scheduled DSMB meeting. The DSMB statistician receives a copy of the random treatment assignment code directly from the study statistician or a second independent statistician not involved with the trial analysis. The DSMB statistician would replace the dummy random treatment code with the actual allocation code and execute the programs. Finally, after reviewing the analysis output and verifying the results, the DSMB statistician would summarize the findings in a report addressed to the other members of the DSMB.

#### 9.4.1.3 *Evidence of benefit*

The interim analysis will consider the using the Haybittle-Peto spending function to determine the test boundaries to preserve the overall two-sided type I error rate of  $\alpha=0.05$  at the final analysis. Overwhelming evidence of benefit will be defined as a p-value favouring the intervention arm of  $<0.001$  after the first or only interim analysis and also a one-sided p-value of  $<0.001$  after the second interim analysis. This test will be conducted using a multilevel regression model with a Poisson likelihood and a log link function which includes random cluster level intercepts. Other models will be considered if there is evidence of overdispersion for Poisson (e.g. negative binomial models). The final null-hypothesis significance testing will be based on an alpha level of 0.049 to control the trial's overall type-I error potential.

#### 9.4.1.4 *Stopping for harm*

The trials do not include formal stopping rules based on harm. The intervention is not targeted to humans, and the expected risk to trial participants is expected to be minimal. However, this does not preclude the DSMB from stopping the trial for harm should unforeseen consequences of the ATSB or trial procedures lead to harms.

#### 9.4.1.5 *Timing of final analysis*

The final analysis will be conducted either following an interim analysis should the trial end early or at the end of two years should no early stopping rule be invoked.

### 9.4.2 **General principles**

#### 9.4.2.1 *Analysis populations*

##### 9.4.2.1.1 *Intention-to-treat population*

The primary analysis of the primary outcome (the incidence of clinical malaria in the cohort) will be conducted with the intention-to-treat analysis population, consisting of all eligible participants recruited and consented to participate in the study.

##### 9.4.2.1.2 *Per-protocol analysis populations*

The per-protocol analysis populations will be those eligible, recruited, and consented participants whose cluster-level adherence meets the definition of adherence. Clusters (and those living in these clusters) will be excluded from the per-protocol population if they fulfil the criteria for non-adherence to ATSB deployment as defined in section 7.7.1, Cluster-level adherence, page 29. The ATSB monitoring data, which are contemporaneously collected, may be used to inform the further definition of the per-protocol population in the statistical analysis plan

#### 9.4.2.1.3 Multiplicity

Whilst the trial tests multiple secondary outcomes, no adjustment will be made of multiplicity because the study has two arms and a single primary outcome. Secondary outcomes are assumed to be on the same causal pathway as the primary outcome.

#### 9.4.2.2 Missing data

##### 9.4.2.2.1 Missing outcome data

Significant effort will be made to reduce missing outcome data by revisiting cohort households multiple times and pre-scheduling follow up visits where possible. When missing data does arise due to failed monthly outcome assessment, no imputation will be used. Full reporting of the fraction of missing outcome assessments by study arm will be conducted for the intention-to-treat study population.

##### 9.4.2.2.2 Missing co-variables

Missing baseline covariables (as defined in the SAP prior to data lock) will be imputed using simple imputation methods based on the covariable distributions, should the missing values for a particular covariable be less than 5%. For a continuous variable, missing values will be imputed from random values from a normal distribution with mean and SD calculated from the available sample. For a categorical variable, missing values will be imputed from random values from a uniform distribution with probabilities  $P_1, P_2, \dots, P_k$  from the sample. The seed for the imputation will be set as a number with eight digitals (e.g. the date of the programming). If the missing values for a covariable are  $\geq 5\%$ , then they will be imputed using Markov chain Monte Carlo (MCMC) methods.

#### 9.4.2.3 Adjusting for cluster design and other correlated observations

For all analyses, standard errors of effect estimates will be estimated with a random intercept at the cluster level to account for correlated observations at the cluster level as a result of the community randomized control trial study design.

### 9.4.3 Analysis of the primary outcome

#### 9.4.3.1 Definition of events and person-time to obtain incidence rates

The primary outcome analysis will be based on a comparison of the unadjusted (crude) incidence rates between study arms using a multi-level (variance compartments model). The incidence rate will be defined as the total number of incident clinical malaria cases divided by the total person-time observed among each cohort.

The person-time (i.e., the denominator) and events (i.e., the numerator) will be defined as follows:

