#### 7.6.3 **Other malaria control interventions**

Community-case management of malaria by community health volunteers is an active intervention promoted by the Ministry of Health in this area. In this strategy, community health volunteers test and treat participants encountered in the households who complain of symptoms compatible with

malaria. Additionally, in September 2019, the Kenya Ministry of Health began a phased implementation of GSK's Mosquirix vaccine in children aged 5-17 months of age. Rarieda sub-county was chosen as an initial vaccinating sub-County, whereas Alego-Usonga was not. To control for the impact of RTS,S/AS01 on our study outcomes, we will ensure a balance of clusters between arms in Rarieda and Alego-Usonga sub-Counties. Additionally, we will record the vaccination status of all children <5 years of age from the maternal-child booklet or from vaccination cards. Where available, we will take a photograph of the child's vaccination records. Where not available, we will use maternal recall. The Kenya Division of National Malaria Program (DNMP) does not currently have plans to perform IRS in Siaya County during the trial period. Should IRS be implemented in the trial area during the trial, the study team will monitor timing and coverage of the campaign at a household and cluster level but will not be responsible for regulating or "topping up" IRS should DNMP initiate spraying in the area.

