### 7.8.1 Malaria case incidence cohort

#### 7.8.1.1 *Main trial*

The sample size was calculated using the 'Tests for the Difference Between Two Poisson Rates in a Cluster Randomized Design' module in PASS 2020 (©NCSS, Kaysville, Utah). The observed event rate in this age group was 1,128 per 1000 person-years in the control arm of a recently completed mass test-and-treat trial in this area. A more conservative event rate of 845/1000 will be used, which is 25% lower than the previously observed event rate of 1,128/1000 person-years. This is done to account for an estimated 7.4% overall reduction in event rates in children 1-<15 years due to the implementation of the RTS,S/AS01E vaccine (vaccine efficacy 39.0%) in two-third of the study area in children 1-<5 years of age (28.6% of the sample study cohort) ( $0.39 \times 0.67 \times 0.286 = 0.074$ ), plus a further 17.6% reduction in malaria due to unforeseen changes in environmental factors, or boosting of other malaria control measures such as the scaling up of integrated community-based case management. The coefficient of variation in this previous study was 0.4.

A total sample size of 2,240 person-years (1,120 per arm, or 28 person-years per cluster) is required to detect a  $\geq 30\%$  reduction in the incidence of clinical malaria among children aged 1-<15 years (the primary outcome) from 845 per 1000 person-years in the control arm to 592 in the intervention arm over two years, allowing for 20% loss of person-time due to LTFU, or exclusion of person time after a clinical event treated with artemether-lumefantrine during a six month follow-up period resulting in 1,760 person-years completed (22 person-years per cluster, 880 person-years per arm) (80 clusters [40 per arm], CV=0.4 in both arms, two-sided  $\alpha=0.049$ , power=90%). No sample size inflation is required two allow for two interim analyses because a similar sample size is needed (2,240) for a study with a final two-sided  $\alpha$  of 0.049 as for a study with a single analysis using a two-sided  $\alpha$  of 0.05.

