The intention is to follow each child for 6.5 months. This includes two weeks of lead-in time that do not contribute to the analysis. These are the first two weeks after the initial presumptive treatment with artemether-lumefantrine to clear any existing parasitaemia. This will then be followed by six months of follow-up time that contribute to the analysis. We will use a more conservative average follow-up time of five months per participant to allow staggered enrolment of participants over time. This means that not all children towards the end of the 2-year trial will complete the full 6.5 months. The 2,240 person-years will thus be obtained by sampling approximately 67.2 individuals for an average of five months each in 80 clusters ( $67.2 \times [5/12] \times 80 = 2,240$ ).

The same sample size will also have 80% power to detect a 26% reduction from 845 to 622 per 1000 person-years with all other parameters kept the same, or 80% power to detect a 30% reduction if the CV was 0.488 instead of 0.4. Similarly, the study would have at least 80.0% power to detect a significant difference at the first interim analysis when 50% of the events have occurred in the control arm if the effect size is 41.2% instead of 30% ( $\alpha=0.001$ , using Haybittle-Peto type boundaries, see 9.4.1, Interim analysis, page 44).

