## 8 METHODS: ASSIGNMENT OF INTERVENTIONS

### 8.1 ALLOCATION AND RANDOMIZATION

Restricted randomization will be used to allocate 80 of the 100 baseline clusters to intervention and control arms for the main trial to minimize any imbalance between study arms on key baseline characteristics. The steps to achieve restricted randomization will be conducted by a study team member who is not responsible for trial implementation. The steps are as follows:

1. Establish balance criteria. The factors described in the table below may be considered for suitability as restriction criteria.
2. Generate a list of at least 100,000 randomizations
3. Check randomizations against balance criteria and drop those that do not fit
4. Assess the number of randomizations left. There may be a need to relax criteria and start again if fewer than 10,000 acceptable randomizations remain.
5. Test remaining set of potential randomizations for validity, specifically that all clusters are being independently assigned to study arms (e.g. check that no two clusters are always jointly assigned to the same arm).
6. Randomly choose a randomisation.
7. Flip a coin to determine if arm A or arm B is ATSB or control.
8. Step 6 and 7 to be done in public with community participation.

Table 3: Factors to consider for restricted randomisation

Covariable/ endpoint	Restriction criteria	Data source	Analytic method
Malaria disease incidence	The difference in mean clinical case incidence between trial arms (size of difference to be assessed when data are available)	Baseline cohort	The difference in disease incidence of cluster summaries between study arms
Bednet use	The difference in mean proportion of persons slept under any net night before survey between trial arms $\leq 5$ percentage points	Baseline survey	The difference in means of cluster summaries of the proportion of persons of all ages slept under any net night before survey between arms

Population	The total population size of the larger trial arm is no more than 10% larger than the smaller arm	Enumeration datasets	Sum(pop size of clusters Arm large)/Sum(Pop size of clusters arm Small) less than 1.10
RTS,S/AS01 vaccinating area	Number of clusters in intervention and control arm balanced by vaccinating or non-vaccinating areas for RTS,S/AS01	Kenya National Vaccinations and Immunizations Programme (NVIP)	N in Arm A == N in Arm B

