9.4.3.2 Computing of incidence rate ratios

To obtain incidence rate ratios, a multi-level variance compartments model will be used, constructed on a generalized linear model framework with a Poisson likelihood and a log link function. Random intercepts will be included for each study cluster, and study arm as a fixed effect coded categorically as 0 for arm A and 1 for arm B. The primary outcome will also be checked for the distributional assumption that the mean and variance of the outcome are similar after conditioning on cluster (e.g. are the within-cluster mean and variance similar). If the variance is substantially larger, a negative binomial likelihood will be considered. Results will be presented as the incidence rate ratio (IRR), 95% confidence intervals and *p*-value.

9.4.3.3 Covariable adjusted analysis of the primary and secondary outcomes:

A secondary co-variable adjusted analysis of the primary outcome will be conducted. Pre-specified covariables, developed and tested prior to final analysis, will be used. It is expected that these will also include the covariables used in restricted randomization (Table 4, below).

Variable	Categorization (if applicable)	Analysis	Analysis Population
Baseline prevalence	Calculated at cluster level	Clinical incidence, prevalence	ITT, per-protocol
Baseline incidence	Calculated at cluster level	Clinical incidence, prevalence	ITT, per-protocol
Rainfall (anomaly)	Summarized monthly at cluster level (lagged one month preceding) as anomaly	Clinical incidence, prevalence	ITT, per-protocol
Season		Clinical incidence, prevalence	ITT, per-protocol
Year	One vs Two	Clinical incidence, prevalence	ITT, per-protocol

Age	Under 60 months vs greater than 60 months	Clinical incidence, prevalence	ITT, per-protocol
-----	-------------------------------------------	--------------------------------	-------------------

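### Clusters are balanced by sub-county/RTS,S area, but the primary and interim models omit area; to the extent area is prognostic, both tests are conservative

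*Protocol*

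**What the plan says.** Protocol section 7.6.3 explains that RTS,S was introduced in Rarieda and not in Alego-Usonga, and that to control for its effect on outcomes "we will ensure a balance of clusters between arms in Rarieda and Alego-Usonga sub-Counties". Table 3 in section 8.1 repeats this as a restriction criterion, "Number of clusters in intervention and control arm balanced by vaccinating or non-vaccinating areas for RTS,S/AS01", and gives the rule as equal numbers in the two arms. The other Table 3 factors are only candidates. The commitment in 7.6.3 makes area balance firm.

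The analysis does not follow that structure. Section 9.4.3.1 says: "The primary outcome analysis will be based on a comparison of the unadjusted (crude) incidence rates between study arms". Section 9.4.3.2 gives the terms: "Random intercepts will be included for each study cluster, and study arm as a fixed effect coded categorically". The interim test in section 9.4.1.3 is "a multilevel regression model with a Poisson likelihood and a log link function which includes random cluster level intercepts", with no area term named. Covariable adjustment (9.4.3.3) is a secondary analysis. It is expected to include the restriction covariables, but Table 4 does not list area.

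**The concern.** When allocation is balanced on a factor that predicts the outcome, that factor's variance no longer contributes to the chance difference between arms. A model without the factor cannot see this. It counts the between-area spread as ordinary cluster-to-cluster variation and puts it in the standard error of the arm effect. The confidence interval is then wider, and the test stricter, than the design warrants.

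The protocol itself treats area as prognostic. Section 7.8.1.1 lowers the expected rate for vaccination in two-thirds of the study area, and section 7.8.2.1.1 uses all-age prevalences of 27.7% in Rarieda and 47.3% in Alego-Usonga.

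The cost would be greatest at the first interim, where the boundary is 0.001. Section 9.4.1.1 says "The purpose of the interim analysis is to use the preliminary data to inform the assessment process" of the WHO advisory group, so precision at that look matters even though crossing the boundary does not by itself stop the trial.

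**Working it through.** **Inputs (section 7.8.1.1).** Control rate 0.845 per person-year; intervention rate 0.845 × 0.70 = 0.5915; 22 person-years per cluster; 40 clusters per arm; CV k = 0.4; two-sided alpha 0.049 (z = 1.969). First interim: half the person-time (11 per cluster), a 41.2% effect (0.845 × 0.588 = 0.4969), and alpha 0.001 taken as two-sided (z = 3.291). Section 7.8.2.1.1 gives the area split as two-thirds and one-third.

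**Reproducing the plan.** Variance of the rate difference = [(λ1 + λ2)/y + k²(λ1² + λ2²)]/40.

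- Final: [1.4365/22 + 0.16 × 1.0639]/40 = [0.0653 + 0.1702]/40 = 0.00589, SE 0.0767. Power = Φ(0.2535/0.0767 − 1.969) = 90.9%, against a planned 90%. The usual cluster-count formula with one added cluster gives 39.9 per arm, against a stated 40.
- First interim: [0.1220 + 0.1537]/40 = 0.00689, SE 0.0830. Power = Φ(0.3481/0.0830 − 3.291) = 81.7%. The plan states that "the study would have at least 80.0% power to detect a significant difference at the first interim analysis" for this effect.

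**Area share of between-cluster variance.** For two areas weighted 2/3 and 1/3, SD = √(2/9) × difference = 0.4714 × difference.

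- Vaccine effect only: 0.39 × 0.286 = 0.1115 lower rate in Rarieda. Mean 0.9256, SD 0.0526, CV 0.057; share 0.057²/0.16 = 2%.
- Child incidence proportional to all-age prevalence (27.7 v 47.3): mean 34.2, SD 9.24, CV 0.270; share 0.270²/0.16 = 46%.

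**Effect of omitting area.** With share f balanced, the true variance uses (1 − f)k² while the crude model reports k². Crude power = Φ((d − z·SE_crude)/SE_true). Adjusted power = Φ(d/SE_true − z). Crude type I = 2[1 − Φ(z·SE_crude/SE_true)] with both rates at 0.845. At f = 46% the final true variance is [0.0653 + 0.54 × 0.1702]/40 = 0.00393, SE 0.0627, and 0.0767/0.0627 = 1.22.

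| Area share | SE too large by | Crude type I (nominal 4.9%) | Final power, crude v adjusted | First-interim power, crude v adjusted |
|---|---|---|---|---|
| 2% | 1.01 | 4.7% | 91.1 v 91.3% | 81.8 v 82.3% |
| 46% | 1.22 | 1.5% | 94.9 v 98.1% | 85.2 v 94.2% |

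**Simulation.** It used 54 + 26 clusters (assumed from the two-thirds/one-third split), equal by arm within area, with gamma cluster effects, Poisson counts and maximum-likelihood fits. There were 20,000 replicates for type I and 10,000 for power. All entries are percentages.

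| Area share | 0 | 2 | 10 | 20 | 46 |
|---|---|---|---|---|---|
| Type I, crude, Wald z | 5.8 | 5.2 | 5.0 | 4.0 | 2.2 |
| Type I, crude, t(78), SE × √(80/78) | 5.1 | 4.6 | 4.3 | 3.5 | 1.9 |
| Type I, arm + area, Wald z | 5.8 | 5.5 | 5.9 | 5.6 | 5.9 |
| Type I, arm + area, t(77), SE × √(80/77) | 5.1 | 4.8 | 5.2 | 4.9 | 5.1 |
| Final power, crude (corrected) | 90.9 | 91.1 | 92.0 | 93.0 | 95.7 |
| Final power, arm + area (corrected) | 90.9 | 91.4 | 93.1 | 95.1 | 98.3 |
| First-interim power, crude (corrected) | 80.4 | 80.9 | 81.3 | 82.3 | 85.3 |
| First-interim power, arm + area (corrected) | 80.3 | 81.4 | 83.9 | 86.6 | 93.9 |

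**Mechanism.** A second simulation used log-normal cluster effects and an area incidence ratio of 47.3/27.7 = 1.71. The crude model's mean SE was 0.100 against an empirical SD of 0.082, and it rejected 1.8% under the null at nominal 4.9%. The same model without area balance rejected 6.0%. The conservatism therefore comes from balancing without adjusting.

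**The case against.** The case on the other side has five parts.

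- **A crude primary with an adjusted secondary is a common, defensible choice.** The sample size was computed for the crude comparison and reproduces, so plan and analysis agree. This stands, and is why the point is one of efficiency only.
- **The size is uncertain.** The only effect built from the protocol's own child-cohort inputs is the 2% share, where adjusting gains almost nothing. The 46% equates all-age prevalence with child clinical incidence, uses a value from neighbouring Karemo, and requires that the CV of 0.4 already contains the area contrast. This also stands. The first-interim gain further assumes a 41.2% effect, larger than the design effect, and crude power there already meets the stated 80%.
- **A crude Wald z test is not conservative at every share.** In simulation it runs at 5.8%, 5.2% and 5.0% for shares of 0, 2 and 10%, because a large-sample test with 80 clusters is slightly liberal and offsets the loss. It falls clearly below nominal only at 20% and above. Like-for-like small-sample corrections show the loss from 2% upward.
- **An adjusted estimate is already foreseen, and the interim boundary is not binding.** Both are true. Neither changes the primary confidence interval or the interim p-value sent to the advisory group. Section 9.4.1.3 lists no fixed effects, so the arm-only reading of the interim model is inferred from its description.
- **Adjusting with an uncorrected Wald test runs above nominal.** This is correct, so the remedy must include a small-sample method.

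**Conclusion.** The concern holds as an efficiency point. The trial commits to balancing by area, then fixes a primary analysis that ignores area and an interim test that names no area term. Omitting area causes no bias and no type I inflation, and the planned 90% power is met either way.

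The loss depends on how strongly area predicts child incidence, which the protocol does not give. Over the assumed range it runs from negligible to about 3 points of power at the final analysis and about 9 points at the first interim. If area is not prognostic there is no loss. The change is worth making because it costs little and aligns the analysis with the allocation.

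**What to change.** In sections 9.4.3.2 and 9.4.1.3, add sub-county/RTS,S area as a fixed effect, so that the model is arm + area + cluster random intercept. Specify inference suited to 80 clusters: for example, the maximum-likelihood standard error multiplied by √(80/77) with a t reference on 77 df, or a cluster-level regression of rates on arm and area with t on 77 df. Report the crude rate ratio as a sensitivity analysis. Other restriction factors actually used may be added if fixed before any unblinded look, with the degrees of freedom reduced to match.

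The cost is a wording change before the first interim, one between-cluster degree of freedom, and a stated small-sample method. That method is essential:

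- **Final analysis:** at area shares of 2% to 46%, an uncorrected Wald test of the adjusted model runs at 5.5% to 5.9% against 4.9%. With six further non-prognostic covariates it runs at 6.7% to 6.9%, while the corrected t(71) gives 4.8% to 4.9%.
- **First interim, nominal 0.1%:** uncorrected 0.155% to 0.197%; corrected t(77) 0.092% to 0.113%.
- **Log-normal cluster effects:** the corrected t(77) gives 5.2% to 5.4% at the final analysis and the cluster-level regression 4.6% to 5.0%, which slightly favours the latter.
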